4 INVESTIGATIONAL PLAN

4.0 Overview of Study Design

This is a randomized double-blind placebo-controlled exploratory study assessing bryostatin for the treatment of moderately severe to severe Alzheimer's disease in subjects not receiving memantine treatment. The study is 15 weeks in duration, including safety and efficacy evaluation 30 days after the last treatment. Eligible subjects will be stratified based on MMSE-2 scores 4-9 vs. 10-15 and will be randomized 1:1 to treatment with 20µg bryostatin or placebo for 12 weeks of

treatment. Study drug is administered IV by continuous infusion. The first two doses of study drug will be a loading dose 20% higher (i.e., 24 μ g) than the assigned dose and will be administered one week apart. Thereafter, the assigned dose of 20 μ g will commence with the third dose and be administered every other week. Subjects are scheduled to receive seven doses over 12 weeks. Safety and efficacy assessments will be done as indicated on the Schedule of Activities (Table 1).

4.1 Dose Rationale

The primary objective of treatment for cognitive disorders with bryostatin is activation of PKC ϵ , not downregulation as was attempted for the oncology indications. Bryostatin activation of PKC ϵ is dose dependent, where lower doses activate PKC ϵ and appear to increase de-novo synthesis of the enzyme, while higher doses of bryostatin downregulate PKC ϵ .

The dosing regimen is based on the recently completed phase 2 study, NTRP101-202, in which the safety and efficacy analyses indicated a clear advantage of the 20 μ g dose over the 40 μ g dose.

The oncology data suggest that the dose-limiting side effect of myalgia is dose dependent and cumulative and likely related to the down regulation of PKC ϵ . This was not seen in the NTRP101-201 study, in which there were no reports of myalgia after a single 25 μ g/m² dose of bryostatin was administered, nor in the recently completed NTRP101-202 study, in which myalgia was considered an adverse event of special interest. In NTRP101-202, in which subjects received 7 doses of study drug, myalgia was seen in 5 subjects; 4 of those subjects were given the higher 40 μ g dose of bryostatin. Myalgia observed was mostly mild and managed with analgesics.

Dosing in this study will begin with two initial loading doses at one-week intervals that are 20% higher than the maintenance dose to assure enzyme activation. Dosing will then continue every other week.

4.2 Risk/Benefit

Bryostatin treatment in study NTRP101-202 was shown to be generally safe and well tolerated. The 20 μ g bryostatin treatment group had similar numbers of TEAEs to the placebo treatment group except in injection site reactions and diarrhea. *Post hoc* analysis in NTRP101-202 clearly showed that bryostatin-treated subjects who did not take memantine at baseline had significantly better improvement in SIB score compared to the placebo group in an MMRM analyses of SIB total score in both the CAS and FAS. Both the pooled bryostatin (20 μ g and 40 μ g) and 20 μ g bryostatin treatment groups had significantly better scores than the placebo treatment group at Weeks 5, 13, and at 30-day Follow-up. There were no statistical differences in SIB score between treatment groups in subjects given memantine at baseline. NTRP101-203 will prospectively seek to replicate these findings and demonstrate a clear benefit both in terms of safety and efficacy in this patient population when comparing the 20 μ g bryostatin dose to placebo.

Therapeutic antibodies targeting β -amyloid have been associated with the occurrence of amyloid related imaging abnormalities (ARIA), which is similar in appearance to cerebral vasogenic edema and microhemorrhage. A minority of cases have been associated with symptoms of headache, visual disturbance, loss of coordination, or disorientation. Asymptomatic ARIA was reported in a clinical study of the small molecule gamma-secretase inhibitor BMS-708163. Bryostatin has a different mechanism of action than antibodies directed at amyloid, but in the transgenic mouse

model of AD treated with bryostatin a decrease of A β deposition was observed. Given the limited bryostatin experience in AD, the potential for ARIA and associated clinical events cannot be excluded. In NTRP101-202, however, there was no clinical evidence suggestive of vasogenic edema or microhemorrhage that required an MRI scan.

Subjects in this study, with moderately severe to severe dementia, are those who have had a progressive dementia to the degree that their activities of daily living and their ability to care for themselves may be compromised. Subjects with MMSE-2 scores of 15 or less display significant cognitive impairments that are disabling. Most if not all of these subjects will have progressed despite treatment and have no alternative treatments available. Based on the available nonclinical and clinical data, and the low risk of ARIA, the potential benefits of treatment with bryostatin at the proposed dose in this protocol outweigh the risks.

4.3 Study Endpoints

4.3.1 Safety Assessments

- Treatment emergent AEs and SAEs
- Vital signs, hematology, blood chemistry, and physical examination including body weight
- ECG parameters
- C-SSRS

4.3.2 Primary Efficacy Endpoint

The primary efficacy endpoint is defined as the change from baseline to Week 13 in the SIB score.

4.3.3 Secondary Efficacy Endpoints

- The changes from baseline at Weeks 5, 9 and 15 in the SIB total score
- The changes from baseline at Weeks 5, 9, 13 and 15 in the SIB total score for subjects in the MMSE-2 4-9 stratification group

The changes from baseline at Weeks 5, 9, 13 and 15 in the SIB total score for subjects in the MMSE-2 10-15 stratification group

- Individual patient's slope over time in SIB evaluated via Weeks 0, 5, 9, and 13.

4.3.4 Exploratory Endpoints

- Change from baseline in Alzheimer's Disease Cooperative Study - Activities of Daily Living – Severe Impairment Version (ADCS-ADL-Sev) total score
- Change from baseline in Mini Mental State Examination, 2nd edition (MMSE-2) total score
- Change from baseline in 10-point Neuropsychiatric Inventory (NPI) total score
- Clinical Global Impression of Improvement Scale (CGI-I) score

4.4 Study Population

Subjects with moderately severe to severe Alzheimer's disease defined as a MMSE-2 score of 4-15 inclusive are eligible to enroll. Subjects will be permitted to continue present FDA-approved treatments for Alzheimer's disease but no new treatments can be initiated. OTC medications taken for cognitive improvement such as Ginkgo Biloba or other empiric medications are permitted while participating in the study but should not be initiated or dose modified after screening. Subjects who are no longer on medications for Alzheimer's disease can be enrolled.

4.4.1 Inclusion Criteria

1. Written informed consent from caregiver and subject (if possible) or legally acceptable representative if different from caregiver
2. Male and female subjects 55-85 years of age inclusive
3. Cognitive deficit present for at least 2 years that meet the diagnostic criteria for probable Alzheimer's dementia.¹⁶ The diagnosis must be confirmed at the time of the screening visit
4. MMSE-2 score of 4-15 inclusive (applies to Screening Visit only)
5. Patients must be able to perform at least one item on the SIB and may not have a SIB score >93 at screening
6. Neuroimaging computerized tomography (CT) or Magnetic Resonance Imaging (MRI) within the last 24 months consistent with a diagnosis of probable AD without any other clinically significant co-morbid pathologies. If there has been a significant change in the subject's clinical status since the last imaging study that is not consistent with progression of the subject's AD, an imaging study should be performed to confirm eligibility
7. Reliable caregiver(s) or informant(s) who attends the subject at least an average of 3 hours or more per day for 3 or more days per week and who will agree to accompany the subject to the clinic visits and reliably complete the caregiver questions
8. Adequate vision and motor function to comply with testing
9. If taking an approved cholinesterase inhibitor for treatment of Alzheimer's disease, must be on a stable dose for at least 3 months prior to entry into study and the dose must not change during the study unless a change is required due to an adverse effect of the prescribed medication or a clinically significant change in the patient's status
10. Subjects who are memantine naïve or have been off memantine for at least 30 days prior to initial treatment with study drug
11. Subjects on neuroleptic medications must be on a stable dose for ≥ 4 weeks (dose adjustments will be permitted)
12. Females participating in the study must meet one the following criteria:
 - a. Surgically sterilized (e.g., hysterectomy, bilateral oophorectomy or tubal ligation) for at least 6 months or postmenopausal (postmenopausal females must have no menstrual bleeding for at least 1 year) or

- b. If not postmenopausal, agree to use a double method of contraception, one of which is a barrier method (e.g., intrauterine device plus condom, spermicidal gel plus condom) 30 days prior to dosing until 30 days after last dose and have negative human chorionic gonadotropin (β -hCG) test for pregnancy at screening
13. Males who have not had a vasectomy must use appropriate contraception methods (barrier or abstinence) from 30 days prior to dosing until 30 days after last dose
14. In the opinion of the PI subjects should be in reasonably good health over the last 6 months and any chronic disease should be stable

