In multiple exploratory analyses adjusting for covariates for the primary endpoint, there were additional significant differences between the placebo treatment group and bryostatin treatment groups. In an MMRM analysis of change from baseline in SIB total score, excluding all subjects from sites that recruited 2 or fewer subjects during the trial, there was a significant difference between the placebo treatment group and the 20µg bryostatin treatment group at Week 5 ($P=0.068$). There was a significant difference between the placebo treatment group and the 20µg

bryostatin treatment group ($P=0.031$), and between the placebo treatment group and the pooled bryostatin treatment group in an MMRM analysis of change from baseline in SIB total score at the 30-day follow up visit ($P=0.041$). When an ANCOVA was performed to assess site effect on SIB, there was a significant difference between the placebo treatment group and 20 μ g bryostatin treatment group ($P=0.032$), and between the placebo treatment group and pooled bryostatin treatment groups ($P=0.049$) at Week 5. In an ANCOVA of change from baseline in SIB total score, with use of AChEI or memantine at baseline as an additional covariate, at Week 5 the 20 μ g bryostatin treatment group and pooled bryostatin treatment groups had statistically significant treatment differences from the placebo treatment group ($P=0.024$ and $P=0.027$, respectively). In multiple exploratory analyses adjusting for covariates for secondary endpoints, there were statistically significant differences between the placebo treatment group and the 20 μ g bryostatin treatment group at Week 5 ($P=0.062$), and the placebo treatment group and pooled bryostatin treatment group at Week 5 ($P=0.041$) when performing an ANCOVA of change from baseline in ADCS-ADL-Sev total score for subjects with > median baseline ADCS-ADL-Sev total score. There was a statistically significant difference between the placebo and 40 μ g bryostatin treatment groups at Week 5 ($P=0.099$) in an ANCOVA of change from baseline in NPI Total score to assess site affects. When performing an ANCOVA of change from baseline in NPI total score for subjects with > median baseline NPI total score, there were statistically significant differences between the placebo treatment group and the 40 μ g bryostatin treatment group at Week 9 ($P=0.054$) and Week 13 ($P=0.096$).

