6.0 Table 1 - Schedule of Activities

		NTRP101-203										
Week	Screening	0	1	2	3	5	7	9	11	13	15/ET	
Day (±2 days)	(Days -28 to -2) ^d	0	7	14	21	35	49	63	77	91	105	
Dose	Rand	1	2		3	4	5	6	7			
Informed Consent	X											
Medical history	X											
Demographics	X											
Rosen-modified Hachinski Scale	X											
SIB	X ^a					X*		X*		X	X	
MMSE-2	X					X*		X*		X	X	
ADCS-ADL-Sev ^b	X					X*		X*		X	X	
NPI ^b	X					X*		X*		X		
CGI-I						X*		X*		X		
CSSRS	X			X			X*			X		
Labs ^{^^}	X			X			X*			X		
ECG	X (x3)			X			X			X		
PE	X						X* ⁺			X		
Vitals	X	X ^c	X ^c	X	X ^c	X ^c	X ^c	X ^c	X ^c	X ^c	X	X
Randomization		X ^a										
Confirm Eligibility	X [◊]	X										
Study Drug Dosing		X	X		X	X	X	X	X			
Adverse Events	X	X	X	X	X	X	X	X	X	X	X	
Con meds	X	X	X	X	X	X	X	X	X	X	X	

^aBaseline SIB administered during screening must be done within 3 weeks of the first dose of study drug. If the screening period exceeds 3 weeks, the SIB should be repeated on the day of first dose, prior to dosing; * before dose; ^^Labs: CBC including differential, coagulation, clinical chemistry, TSH at screening (B12, T-3 and T-4 if TSH abnormal), CPK at screening and event of myalgia, βhCG if indicated, HbA1C if clinically indicated; [◊] CT scan if necessary per inclusion criterion #6; ⁺ abbreviated physical examination; ^a Randomization after initial screening procedures indicate eligibility; ^b The ADCS-ADL-Sev and NPI may be administered via telephone at the discretion of the investigator, within the allowed time window for the scheduled visit; ^c Vital signs prior to infusion, then at 30, 60 and 90 minutes from start of the infusion (+/- 5min). ^dThe visit window of ±2 Days does not apply to the Screening and Randomization period which is a maximum of 28 days.

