6.2 Visit Procedures

6.2.1 Screening and Randomization (Days -28 to -2)

In order to avoid unnecessary screen failures, a prescreening telephone call to rule out clearly exclusionary conditions is advised prior to scheduling a screening visit. Informed Consent must be obtained before any study related procedures are performed. Screening procedures and randomization will take place within an approximate 4-week period prior to first dose administration (Days -28 to -2).

Subjects who are screen-failed (e.g. due to clinically significant laboratory abnormality or an active medical condition) may be re-screened if their medical condition stabilizes or improves as assessed by the PI. Subject who are screen-failed due to MMSE score may be rescreened in 3 months.

The Medical Monitor should be consulted prior to re-screening. Subjects who are Screen Failures may be rescreened only once.

The following procedures should be performed first to avoid unnecessary procedures for ineligible subjects:

- Collection of subject demographic data
- Review of concomitant medications

- Review of medical history
- Assessment of neuroimaging (CT or MRI performed within 2 years of screening)
- Evaluate Rosen-Modified Hachinski Scale
- Evaluate MMSE-2

After confirming that these parameters satisfy eligibility criteria, the remaining screening procedures should be performed;

- SIB. The SIB should be done within 3 weeks before the first study drug dose. If the screening period exceeds 3 weeks, the SIB should be repeated on the day of the first dose, prior to dosing. The repeat SIB score obtained closest to the day of dosing should be recorded in the eCRF as an unscheduled visit.
- NPI
- ADSC-ADL-SIV
- Columbia Suicide Severity Rating Scale (C-SSRS)
- Blood samples for routine safety including hematology, PT, PTT, INR and serum-chemistry, CPK, TSH (B12, T-3 and T-4 if indicated), and β -hCG, if indicated
- 12-lead ECG (x3)
- Complete physical examination
- Vital signs
- AEs and concomitant medications

If changes in the subject's health or mental status occur during the screening and randomization period, including changes in medication affecting the mental status, the Medical Monitor should be notified. The Medical Monitor will advise the PI regarding any assessments that should be repeated to ensure eligibility requirements are met.

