6.3.3 Prohibited Medications

Memantine is prohibited. Subjects previously treated with memantine must stop treatment at least 30 days prior to initiation of study drug treatment. Treatment with other NMDA receptor antagonists such as but not limited to dextromethorphan (a cough suppressant), ketamine, phencyclidine (PCP), methoxetamine (MXE), nitrous oxide (N₂O) and the following synthetic opioids: pentidine, levorphanol, methadone, dextropropoxyphene, tramadol, and ketobemidone is prohibited and a 30-day washout period is required prior to initiation of study drug treatment.

High dose Vitamin E (> 400 IU / day), Valproic Acid and divalproex sodium are prohibited.

If the PI determines that initiation of any of the prohibited medications is required to ensure the subject's safety, the medication may be initiated with the notification of the Medical Monitor and proper documentation of a protocol deviation. Other restricted concomitant medications are listed in Appendix 1.

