7. DATA CONVENTION AND RELATED DEFINITIONS

7.1 Baseline Definition

For all parameters, baseline will be defined as the last available value before the randomized treatment.

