8.2.1 Primary Efficacy Endpoint

The primary endpoint for this study is the change from baseline to Week 13 in the SIB total score.

The change from baseline to Week 13 in the SIB total score will be summarized descriptively and compared using Analysis of Covariance (ANCOVA) adjusted for baseline SIB total score.

If the normality assumption is not met, a non-parametric method or a rank-ANCOVA analysis (i.e., an ANCOVA analysis on rank-transformed data) will be used.

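### The memantine washout runs to first dose but the baseline SIB may be taken 21 days earlier, so baseline can fall 9 days after stopping, and the primary model has no term for recent memantine use

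*Protocol*

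**What the plan says.** **Washout.** Inclusion criterion 10 (Protocol 4.4.1) takes subjects who have never used memantine or who "have been off memantine for at least 30 days prior to initial treatment with study drug". Protocol 6.3.3 uses the same anchor: "Subjects previously treated with memantine must stop treatment at least 30 days prior to initiation of study drug treatment". Both count back from the first infusion.

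**Baseline SIB.** Screening may last up to 28 days. Protocol 6.2.1 states: "The SIB should be done within 3 weeks before the first study drug dose". The footnote to Table 1 (Protocol 6.0) adds: "If the screening period exceeds 3 weeks, the SIB should be repeated on the day of first dose, prior to dosing". Under SAP 7.1, "baseline will be defined as the last available value before the randomized treatment". A screening SIB on Day −21 with no repeat is therefore the baseline. Neither document sets a minimum time off memantine before the baseline SIB.

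**Analysis.** Under SAP 8.2.1 the Week 13 change is "compared using Analysis of Covariance (ANCOVA) adjusted for baseline SIB total score". SAP 7.6 permits further baseline covariates without committing to any, and does not mention memantine. MMSE-2 group is the only stratification factor (SAP 7.7) and the only covariate named for the imputation models (SAP 7.3.1).

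**Data available.** Protocol 6.3 collects a 6-month medication history at screening, and SAP 8.1.3 summarises prior medications by arm.

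**The concern.** The baseline SIB should describe the subject in the state from which change is measured. For someone who has just stopped memantine it may not. If the drug was still supporting cognition when the SIB was taken, its later loss would be counted as change on study. Adjusting for the baseline score does not remove a decline that happens after baseline in some subjects and not in others.

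Memantine status is also the premise of this trial, which seeks to replicate a post hoc result in study 202 subjects who were not taking memantine at baseline (Protocol 4.2). At stake are some precision in the primary comparison and a foreseeable question about the variable that defines the population, with no prespecified analysis to answer it.

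**Working it through.** **1. Shortest interval from stopping memantine to baseline SIB.** Latest permitted stop: Day −30. Earliest SIB that needs no repeat: Day −21. Interval = 30 − 21 = 9 days. This is the limiting case, because a later SIB or an earlier stop lengthens it. If screening exceeds 3 weeks, the Day 0 repeat becomes the baseline, at least 30 days after stopping.

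**2. The plan's own power.** Inputs from Protocol 9.0 and SAP 3: SDs 6.8 and 6.7, two-sided α = 0.05, two-sample t-test. Pooled SD = √((6.8² + 6.7²)/2) = √45.565 = 6.75. The noncentral t-distribution gives:

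| Difference (points) | 50 per arm: stated | 50 per arm: recomputed | 37 per arm: stated | 37 per arm: recomputed |
|---|---|---|---|---|
| 4.0 | 83% | 83.5% | – | – |
| 4.5 | 91% | 91.0% | 80% | 80.8% |
| 5.0 | 95% | 95.6% | 88% | 88.2% |
| 5.5 | 98% | 98.1% | 93% | 93.3% |

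The stated figures reproduce.

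**3. What a withdrawal effect would do.** Let a share f of each arm be recent stoppers with a mean extra decline of w SIB points after baseline. The documents give neither value, so both are assumed. Outcome variance becomes 45.565 + f(1 − f)w².

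| f | w | Added variance | SD | Power, 4.0 points, 50 per arm | Power, 4.5 points, 37 per arm |
|---|---|---|---|---|---|
| 0 | – | 0 | 6.75 | 83.5% | 80.8% |
| 5% | 2 | 0.19 | 6.76 | 83.3% | 80.6% |
| 5% | 4 | 0.76 | 6.81 | 82.9% | 80.1% |
| 10% | 2 | 0.36 | 6.78 | 83.2% | 80.5% |
| 10% | 4 | 1.44 | 6.86 | 82.3% | 79.5% |
| 50% | 4 | 4.00 | 7.04 | 80.3% | 77.4% |

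The mean change falls by f × w in both arms alike: 0.1 to 0.4 points for f of 5–10%, and 2.0 points in the last row. In expectation it cancels from the treatment difference.

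**4. Chance imbalance is part of the same variance.** The standard error of the difference due to unequal numbers of recent stoppers is w√(2f(1 − f)/50). In the last row this is 4 × √(0.5/50) = 0.40. Without any withdrawal effect, the standard error of the treatment difference is 6.75 × √(2/50) = 1.35. Combined: √(1.35² + 0.40²) = 1.408, which equals 7.04 × √(2/50). Imbalance is therefore already in the larger SD and must not be added to the power loss as a second harm.

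**The case against.** The strongest objection is that the mechanism is assumed. Neither document reports a decline in SIB after stopping memantine. The post hoc result in Protocol 4.2 concerns response to bryostatin by memantine use, which is a different matter. This stands: the material shows that the timing is possible and the covariate absent, not that harm follows.

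Three further points stand.

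- **Who is affected.** The mechanism needs a stop shortly before the baseline SIB. Applying several points of decline to every former user, including those off the drug for a long time, would overstate the effect. Hence the 5–10% range, with 50% only as an extreme.
- **Planning SD.** The 6.8 and 6.7 come from study 202 subjects defined by no memantine use at baseline, not by never having used it. They may already contain some of this variance; the documents cannot settle it.
- **Precedent.** Study 202 included an ANCOVA "with use of AChEI or memantine at baseline as an additional covariate" (Protocol 2.1.5). A reader might infer that the sponsor has already accepted the adjustment proposed here. It was one of several exploratory analyses and concerned current use, whereas here nobody may be on memantine at first dose.

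Two points of mitigation stand only in part. SAP 7.6 would allow the covariate, but permission is not prespecification. The by-arm medication summary would show an imbalance but would not adjust for it.

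**Conclusion.** The plan allows a baseline SIB 9 days after memantine is stopped, and the primary model has no term for recent use. That much follows directly from the documents.

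A reader might go further and infer that withdrawal effects do enter the primary result and bias it. The documents do not support this. They show no such effect, and randomisation makes the share of recent stoppers equal across arms in expectation. Nor is a chance imbalance a distortion beyond the reported standard error.

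What remains is a possible small loss of precision. With 5–10% recent stoppers and 2–4 points of extra decline, the loss for a 4.0-point effect with 50 per arm is 0.2 to 1.2 percentage points of power. Even at 50% and 4 points power stays just above 80%. With 37 per arm and a 4.5-point effect the plan's margin over 80% is under one point, so it is lost at 10% and 4 points (79.5%). All of this rests on assumed values of f and w. The point is a low-priority improvement, worth making because it is cheap.

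**What to change.** Before unblinding:

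1. **SAP 8.2.1 and 7.3.1.** Name memantine use within the 6 months before screening (yes/no) as a covariate in the primary ANCOVA and in the imputation model. The history in Protocol 6.3 can supply this. It cannot separate never-users from those who stopped more than 6 months earlier, so a never-versus-stopped factor should not be used. The yes/no factor still groups very recent stoppers with those some months off the drug, so it captures the mechanism only in part.
2. **SAP 8.2.1.** Report the treatment effect by this factor, descriptively.
3. **Protocol 6.0 and 6.2.1.** Reconcile the two anchors by extending the Day 0 pre-dose repeat SIB to subjects whose screening SIB fell within 30 days of stopping memantine. SAP 7.1 would then take the repeat as baseline without further change. No washout length is proposed.

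Items 1 and 2 are SAP wording and cost one model degree of freedom. Item 3 is a small change to the protocol schedule. It adds one SIB, with a possible practice effect, in a few subjects, equal across arms in expectation. If recruitment is too far advanced for item 3, items 1 and 2 still stand on their own.
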